- If the EASI score at the End of Treatment/Early Termination Visit is lower than the EASI score at the Baseline Visit (ie, improvement in AD severity), then medications prohibited

during treatment period (Day 1 to 29; see Section 5.8.2) are prohibited until the completion of the Day 43 Visit.

- After the end of treatment, and prior to the Day 43 visit, unscheduled clinic visits are available if subject's condition worsens, so that an assessment can be conducted in-clinic, and nonstudy treatment intervention prescribed as necessary. If the EASI score at this unscheduled visit is the same or higher than the EASI score at the Baseline Visit (ie no improvement or worsening of AD severity) there are no restrictions to medications used to treat AD. After the Day 43 visit, there are no restrictions to medications used to treat AD, except for subjects participating in the sub-study (Appendix 4).

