6.4.5. Unscheduled Visit

The procedures performed at an Unscheduled Visit will depend on the reason for the visit (some procedures may not apply).

- Obtain vital signs (temperature, respiratory rate, pulse rate, and BP) in the seated or supine position, preferably after the subject has been sitting or lying face up for a minimum of 5 minutes (when possible for younger children);
- Assess and record any changes in concomitant medications, including confirming that subject is not taking any prohibited medications, as detailed in [Section 5.8.3](#);
- Unblinded personnel to instruct the subject and/or caregiver regarding all procedures for at home dosing beginning BID dosing through Day 29 visit, including how to complete the dosing diary;
- Unblinded personnel must remind the subject not to discuss any element of the Investigational product with the blinded assessor, including study drug appearance;
- Unblinded personnel should check for any residue of Investigational product. If any Investigational product is visible, it is permissible to gently remove it prior to the assessments performed by the clinical assessor blinded to treatment arms to avoid potential unblinding;
- Review the schedule of upcoming study visits with the subject and/or caregiver, and instruct them to return at the scheduled time;
- Assess and record any AEs and SAEs by a clinical assessor blinded for treatment arms. Other site personnel may also report and record AEs and SAEs reported to them spontaneously by the subject.
- After the end of treatment, unscheduled clinic visits are available if subject's condition worsens, so that an assessment can be conducted in-clinic, and nonstudy treatment for AD may be prescribed if the subject qualified for this treatment. At this visit, an EASI assessment completed by a clinical assessor blinded for treatment arms will be completed to determine if treatment is allowed per the protocol. If a subject is participating in the sub-study, all efforts should be made not to treat the sub-study target skin sites until after the end of the follow up phase (Day 60).

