3. ENDPOINTS AND BASELINE VARIABLES: DEFINITIONS AND CONVENTIONS

3.1. Primary Endpoint(s)

3.1.1. Efficacy Endpoint

The primary efficacy endpoint is:

- Percent change from baseline in EASI total score at Day 29.

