9. APPENDICES

Appendix 1. Definition and Use of Visit Windows in Reporting

Visit windows will be used for efficacy variables, and for any safety data that display/summarize by study visit.

Visit Label	Target Day	Definition [Day window]
Screening		Days -35 to Day -1
Baseline	Day 1, Baseline	Day 1*
Day 8	8	Days 2 to 11
Day 15	15	Days 12 to 18
Day 22	22	Days 19 to 25
Day 29/ End of Treatment/ Early Termination	29	Days 26 to last dose +7
Day 43	43	Last dose +8 to end of study

* The baseline of Peak pruritus NRS/scale and **CCI** is the average of 7-day scores immediately prior to Day 1 (Day -6 to Day 1)

For the lab values, if the calculated study Day for the labelled baseline visit is not study Day 1 but falls within 28 days before the start of the study dosing, then that data should be used for the baseline instead of leaving baseline missing.

For the other values, if the calculated study day for the labelled baseline visit is not study Day 1, but falls before the start of the study dosing, then that data should be used for the baseline instead of leaving baseline missing.

If two or more visits fall into the same window, keep the one closest to the Target Day. If two visits are equaled distant from the Target Day in absolute value, the later visit should be used.

Safety analysis may follow Pfizer standards.

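### SAP Appendix 1 does not protect the scheduled end-of-treatment EASI: read literally, a later unscheduled worsening visit can replace it as the Day 29 value when the scheduled visit fell on Day 26, 27 or 28.

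*SAP*

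**What the plan says.** The primary efficacy endpoint in SAP 3.1.1 is "Percent change from baseline in EASI total score at Day 29". Which assessment counts as Day 29 is settled in SAP Appendix 1:

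- Scope: "Visit windows will be used for efficacy variables, and for any safety data that display/summarize by study visit".
- Day 29 / End of Treatment / Early Termination row, target Day 29: "Days 26 to last dose +7".
- Day 43 row: "Last dose +8 to end of study".
- Selection: "If two or more visits fall into the same window, keep the one closest to the Target Day".
- Ties: "If two visits are equaled distant from the Target Day in absolute value, the later visit should be used".

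The appendix does not mention unscheduled visits, and it does not rank a scheduled assessment above another in the same window.

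The protocol supplies the rest. The end-of-treatment visit may take place on Day 29 ± 3 days (6.2, 6.4.3). If it is moved, dosing continues to the evening before it (5.5 and the Schedule of Activities). Section 5.8.4 adds: "After the end of treatment, and prior to the Day 43 visit, unscheduled clinic visits are available if subject's condition worsens". Section 6.4.5 says that at such a visit "an EASI assessment completed by a clinical assessor blinded for treatment arms will be completed to determine if treatment is allowed" under the protocol.

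**The concern.** A completer whose end-of-treatment visit came a little early, and who returned within days because the eczema seemed worse, has two EASI values in the Day 29 window. The appendix picks between them by distance from Day 29 alone. The later value can win, although the scheduled one was taken as planned the day after the last dose.

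The replacing value differs in two ways. It is read further off drug, and it exists only because the disease was thought to have worsened. Three summaries kept in SAP version 3 would carry it: the Day 29 EASI percent change (6.1.1, and its subgroup breakdown in 6.4), EASI75 at Day 29 (6.1.5) and the percent change from Day 29 to Day 43 (6.1.2). In the last of these, a relapse value used as the starting point would hide part of the off-treatment worsening that the summary should show. SAP 5.3.2 uses observed data for continuous endpoints, so a wrongly chosen value enters the mean directly.

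**Working it through.** **Inputs.** End-of-treatment day E from 26 to 32 (Protocol 6.2). Last dose L = E − 1 (Protocol 5.5). Day 29 window from Day 26 to L + 7 = E + 6, nearest visit kept, later visit on a tie (SAP Appendix 1).

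**The plan's own figure.** Protocol 9.1 assumes 150 subjects per arm, a 12-point difference and SD 34. The standard error is 34 × √(2/150) = 3.93, and 12/3.93 − 1.96 = 1.10, which gives power of 0.86. This agrees with the stated 86%. The point below does not depend on it.

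**Do scheduled visits collide?** The protocol windows are Days 7-9, 12-18, 19-25 and 26-32. Each lies inside its own Appendix 1 row (Days 2-11, 12-18, 19-25, 26 onwards). The one scheduled overlap in the Day 29 row is a Day 38 follow-up after a Day 32 end-of-treatment visit (L + 7 = 38). It is 9 days from target against 3, so it cannot displace the end-of-treatment value. For subjects on schedule, any visit that displaces it must therefore be unscheduled.

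**When does a later visit win?** A visit on day U, with E < U ≤ E + 6, replaces the end-of-treatment value if |U − 29| ≤ |E − 29|. For E < 29 this means U ≤ 58 − E. For E ≥ 29 any later visit is further from target and loses.

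| End-of-treatment day | Last dose | Window | Replaced by a visit on | Days after last dose |
|---|---|---|---|---|
| 26 | 25 | 26-32 | 27-32 (32 by tie) | 2-7 |
| 27 | 26 | 26-33 | 28-31 (31 by tie) | 2-5 |
| 28 | 27 | 26-34 | 29-30 (30 by tie) | 2-3 |
| 29-32 | 28-31 | 26 to 35-38 | none | – |

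If the last dose fell on the end-of-treatment day itself, the replacing days would be the same, at 1-6 days after last dose.

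**Size.** The documents give no flare rate, so what follows is an illustration. Protocol 9.1 plans mean improvements of 38.9% and 26.8%, a difference of 12.1. Suppose a fraction f of values is replaced by 0% change.

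- Same f in both arms: the difference becomes (1 − f) × 12.1. For f = 1% it is 11.98, and for f = 2% it is 11.86, a loss of 0.12 to 0.24 points.
- Crisaborole only: 38.9 × (1 − f) − 26.8. For f = 1% it is 11.71, and for f = 2% it is 11.32.

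**At the enrolment reached.** SAP 5.1 puts enrolment at 40% of plan: 0.40 × 600 = 240. If the 1:1:2 ratio held, the combined crisaborole group has about 240/4 = 60 subjects. One value moved from 38.9 to 0 shifts its mean by 38.9/60 = 0.65 points, against a standard error of 34/√60 = 4.4. In a single-cohort crisaborole group, reported separately under SAP 5.2 and about 30 subjects if the cohorts are equal, the shift is 38.9/30 = 1.3 points. One lost EASI75 responder there is 1/30 = 3.3 percentage points.

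**The case against.** The best reply is that Appendix 1 is silent on unscheduled visits, and silence is not a rule. SAP 3.2.1 defines the visit-based secondary endpoints by scheduled time points, and SAP 5.3.1 treats binary endpoints at each scheduled visit. A programmer might well leave unscheduled assessments out. That is fair as far as it goes, and a reader should not infer that the SAP deliberately requires replacement. But that wording names the time points to be reported, not which assessments may fill a window. The windows apply to efficacy variables without restriction, and the selection rule speaks of visits in general.

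Other parts of the reply stand and limit the point:

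- **Direction.** It is tempting to say that the error always lowers the apparent effect. The documents do not support that. Perceived worsening need not mean a higher EASI. Under Protocol 5.8.4, a subject with no improvement at end of treatment has no restriction on AD medication, so a later EASI could be lower.
- **Other medication.** A reader might infer that the replacing value is generally contaminated by other AD treatment. For subjects who improved, the restrictions continue to Day 43, and the unscheduled EASI is itself the test for lifting them. It would therefore normally come before any new treatment.
- **Exposure.** Spreading visits evenly over Days 26-32 would expose 3/7 of completers. The protocol, however, treats a move from Day 29 as an exception, so the true share is probably lower.
- **Off drug.** The scheduled value also follows the last dose, by one day. The issue is the extra days and the selection on worsening.

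**Conclusion.** The point holds as a defect in the selection rule. On its literal reading, Appendix 1 can replace a valid end-of-treatment EASI from Day 26, 27 or 28 with one taken 2-7 days after the last dose, at a visit made because the disease seemed worse. The error runs mainly, but not always, towards less improvement.

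The consequence is limited. A reader might infer bias in the primary comparison, but SAP 5.1 drops all testing after termination and keeps descriptive summaries only, so no p-value or decision is affected. The outputs at risk are the Day 29 EASI percent change, EASI75 at Day 29 and the Day 29 to Day 43 EASI change, probably through very few subjects. Equal replacement of about 1-2% in both arms would move the planned 12-point difference by only about 0.1 to 0.25 points. That rate, and the setting of replaced values to no change, are assumptions. The list of replacing days follows from the documents, given that unscheduled visits enter the windows.

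**What to change.** Add to SAP Appendix 1 that a scheduled End-of-Treatment/Early Termination assessment falling in the Day 29 window takes priority over any other visit in that window. Add that unscheduled post-treatment EASI values are listed separately and do not replace it. The number of replacing days then falls from 6, 4 and 2 (end of treatment on Day 26, 27 and 28) to zero.

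The cost is about one sentence of SAP wording and a small programming change. Sample size and the use of scheduled data are untouched. If exclusion of unscheduled visits was always intended, the sentence only records it. Stricter conditions, such as a cut-off in days since last dose for subjects without an end-of-treatment assessment, are not needed to cure this defect.

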Appendix 2. Investigator's Static Global Assessment (ISGA)

The ISGA, a five-point global assessment of AD severity, will be assessed at times specified in the Study Procedure section of study protocol to characterize subjects' overall disease severity across all treatable AD lesions (excluding the scalp).

The ISGA will be a static evaluation without regard to the score at a previous visit. It must be completed by a clinical assessor blinded for treatment arms. Every effort should be made to ensure that all ISGA assessments for a given subject are done by the same qualified individual throughout the study.

ISGA Score

Score	Grade	Definition
0	Clear	Minor residual hypo/hyperpigmentation; no erythema or induration/papulation; no oozing/crusting
1	Almost Clear	Trace faint pink erythema, with barely perceptible induration/papulation and no oozing/crusting
2	Mild	Faint pink erythema with mild induration/papulation and no oozing/crusting
3	Moderate	Pink-red erythema with moderate induration/papulation with or without oozing/crusting
4	Severe	Deep or bright red erythema with severe induration/papulation and with oozing/crusting

* The ISGA will exclude scalp from the assessment/scoring.

Appendix 3. Eczema Area and Severity Index (EASI)

The EASI quantifies the severity of a subject's AD based on both severity of lesion clinical signs and the percent of BSA affected. EASI is a composite scoring of the degree of erythema, induration/papulation, excoriation, and lichenification (each scored separately) for each of four body regions, with adjustment for the percent of BSA involved for each body region and for the proportion of the body region to the whole body.

Lesion Severity by Clinical Signs: The basic characteristics of atopic dermatitis lesions erythema, induration/papulation, excoriation, and lichenification provide a means for assessing the severity of lesions. Assessment of these four main clinical signs is performed separately for four body regions: head and neck, upper limbs, trunk (including axillae and groin) and lower limbs (including buttocks). Average erythema, induration/papulation, excoriation, and lichenification are scored for each body region according to a 4 point scale: 0=absent; 1=mild; 2=moderate; 3=severe. Morphologic descriptors for each clinical sign severity score are shown in the table below.

Clinical Sign Severity Scoring Criteria for the EASI

Score		Description
Erythema (E)		
0	Absent	None; may have residual discoloration (post-inflammatory hyperpigmentation and/or hypopigmentation).
1	Mild	Light pink to light red
2	Moderate	Red
3	Severe	Deep, dark red
Induration/Papulation (I)		
0	Absent	None
1	Mild	Barely palpable to slight, but definite hard thickened skin and/or papules
2	Moderate	Easily palpable moderate hard thickened skin and/or papules
3	Severe	Severe hard thickened skin and/or papules
Excoriation (Ex)		
0	Absent	None
1	Mild	Slight, but definite linear or picked scratch marks or penetrating surface injury
2	Moderate	Moderate linear or picked scratch marks or penetrating surface injury
3	Severe	Severe linear or picked scratch marks or penetrating surface injury
Lichenification (L)		
0	Absent	None
1	Mild	Barely perceptible to slight, but definite thickened skin, fine skin markings, and lichenoid scale
2	Moderate	Moderate thickened skin, coarse skin markings, and coarse lichenoid scale
3	Severe	Severe thickened skin with very coarse skin markings and lichenoid scale
* The EASI will exclude scalp from the assessment/scoring		

%BSA with Atopic Dermatitis: The number of handprints of AD skin in a body region can be used to determine the extent (%) to which a body region is involved with atopic dermatitis.

Handprint Determination of Body Region Surface Area for Subjects ≥ 8 Years

Body Region	Total Number of Handprints in Body Region	Surface Area of Body Region Equivalent of One Handprint
Head and Neck	10	10%
Upper Limbs	20	5%
Trunk (including axillae)	30	3.33%
Lower Limbs (including buttocks)	40	2.5%

Handprint Determination of Body Region Surface Area for Subjects < 8 Years

Body Region	Total Number of Handprints in Body Region*	Surface Area of Body Region Equivalent of One Handprint
Head and Neck	20	5%
Upper Limbs	20	5%
Trunk (including axillae)	30	3.33%
Lower Limbs (including buttocks)	30	3.33%

The extent (%) to which each of the four body regions is involved with AD is categorized using a non-linear scaling method to a numerical area score according to the following BSA scoring criteria.

Eczema Area and Severity Index (EASI) Area Score Criteria

Percent Body Surface Area (BSA) with Atopic Dermatitis in a Body Region	Area Score
0%	0
>0-<10%	1
10-<30%	2
30-<50%	3
50-<70%	4
70-<90%	5
90-100%	6

Body Region Weighting: Each body region is weighted according to its approximate percentage of the whole body.

EASI Body Region Weighting

Body Region	Body Region Weighting for Subjects ≥ 8 Years	Body Region Weighting for Subjects < 8 Years
Head and Neck	0.1	0.2
Upper Limbs	0.2	0.2
Trunk (including axillae)	0.3	0.3
Lower Limbs (including buttocks)	0.4	0.3

In each body region, the sum of the Clinical Signs Severity Scores for erythema, induration/papulation, excoriation, and lichenification is multiplied by the Area Score and by the Body Region Weighting to provide a body region value, which is then summed across all four body regions resulting in an EASI score as described in equations below.

Equation 1 (subjects ≥ 8 years old): EASI = 0.1Ah(Eh+Ih+Exh+Lh) +
0.2Au(Eu+Iu+Exu+Lu) + 0.3At(Et+It+Ext+Lt) + 0.4Al(El+Il+Exl+Ll)

Equation 2 (subjects 2-<8 years old): EASI = 0.2Ah(Eh+Ih+Exh+Lh) +
0.2Au(Eu+Iu+Exu+Lu) + 0.3At(Et+It+Ext+Lt) + 0.3Al(El+Il+Exl+Ll)

A=Area Score; E=erythema; I=induration/papulation; Ex=excoriation; L=lichenification; h=head and neck; u=upper limbs; t=trunk; l=lower limbs.

The EASI score can vary in increments of 0.1 and range from 0.0 to 72.0, with higher scores representing greater severity of AD. Since the scalp will be excluded from the EASI assessment in this study, the maximum possible score will be less than 72.0.

Appendix 4. Dermatology Life Quality Index (DLQI)

<http://sites.cardiff.ac.uk/dermatology/quality-of-life/dermatology-quality-of-life-index-dlqi/dlqi-instructions-for-use-and-scoring/>

The Dermatology Life Quality Index questionnaire is designed for use in adults, ie, patients aged 16 years and over. It is self explanatory and can be simply handed to the patient who is asked to fill it in without the need for detailed explanation. It is usually completed in one to two minutes.

The aim of this questionnaire is to measure how much your skin problem has affected your life OVER THE LAST WEEK. Please tick one box for each question.

1.	Over the last week, how itchy, sore, painful or stinging has your skin been?	Very much A lot A little Not at all	
2.	Over the last week, how embarrassed or self conscious have you been because of your skin?	Very much A lot A little Not at all	
3.	Over the last week, how much has your skin interfered with you going shopping or looking after your home or garden ?	Very much A lot A little Not at all	Not relevant
4.	Over the last week, how much has your skin influenced the clothes you wear?	Very much A lot A little Not at all	Not relevant
5.	Over the last week, how much has your skin affected any social or leisure activities?	Very much A lot A little Not at all	Not relevant
6.	Over the last week, how much has your skin made it difficult for you to do any sport ?	Very much A lot A little Not at all	Not relevant
7.	Over the last week, has your skin prevented you from working or studying ?	Yes No	Not relevant
	If "No", over the last week how much has your skin been a problem at work or studying ?	A lot A little Not at all	
8.	Over the last week, how much has your skin created problems with your partner or any of your close friends or relatives ?	Very much A lot A little Not at all	Not relevant

9.	Over the last week, how much has your skin caused any sexual difficulties ?	Very much A lot A little Not at all	Not relevant
10.	Over the last week, how much of a problem has the treatment for your skin been, for example by making your home messy, or by taking up time?	Very much A lot A little Not at all	Not relevant

Scoring

The scoring of each question is as follows:

Response	Score
Very much	scored 3
A lot	scored 2
A little	scored 1
Not at all	scored 0
Not relevant	scored 0
Question unanswered	scored 0
Question 7: "prevented work or studying"	scored 3

The DLQI is calculated by summing the score of each question resulting in a maximum of 30 and a minimum of 0. The higher the score, the more quality of life is impaired. The DLQI can also be expressed as a percentage of the maximum possible score of 30.

****Please Note:** That the scores associated with the different answers should not be printed on the DLQI itself, as this might cause bias**

Meaning of DLQI Scores

- 0-1 = no effect at all on patient's life
- 2-5 = small effect on patient's life
- 6-10 = moderate effect on patient's life
- 11-20 = very large effect on patient's life
- 21-30 = extremely large effect on patient's life

Detailed analysis of the DLQI

The DLQI can be analysed under six headings as follows:

Section	Questions	Score
Symptoms and feelings	Questions 1 and 2	Score maximum 6
Daily activities	Questions 3 and 4	Score maximum 6
Leisure	Questions 5 and 6	Score maximum 6
Work and School	Question 7	Score maximum 3
Personal relationships	Questions 8 and 9	Score maximum 6
Treatment	Question 10	Score maximum 3

The scores for each of these sections can also be expressed as a percentage of either 6 or 3.

Interpretation of incorrectly completed questionnaires

There is a very high success rate of accurate completion of the DLQI. However, sometimes subjects do make mistakes.

1. If one question is left unanswered this is scored 0 and the scores are summed and expressed as usual out of a maximum of 30.
2. If two or more questions are left unanswered the questionnaire is not scored.
3. If question 7 is answered 'yes' this is scored 3. If question 7 is answered 'no' but then either 'a lot' or 'a little' is ticked this is then scored 2 or 1. If "Not relevant" is ticked, the score for Question 7 is 0. If it is answered 'no', but the second half is left incomplete, the score will remain 0.
4. If two or more response options are ticked, the response option with the highest score should be recorded.
5. If there is a response between two tick boxes, the lower of the two score options should be recorded.
6. The DLQI can be analysed by calculating the score for each of its six sub-scales (see above). When using sub-scales, if the answer to one question in a sub-scale is missing, that sub-scale should not be scored.

Minimal Clinically Important Difference of the DLQI

For **general inflammatory skin conditions** a change in DLQI score of at least 4 points is considered clinically important (Basra et al, 2015, see below). This means that a patient's DLQI score has to either increase or decrease by at least 4 points in order to suggest that there has actually been a meaningful change in that patient's quality of life since the previous measurement of his/her DLQI scores.

Key References

Original Reference

[figure not shown]

